1.1. Synopsis

Study Title	Assessment study of the AIDAVA prototype which aims to improve the quality of clinical data, for their reuse in clinical care in patients with established cardiovascular diseases, and in clinical research for breast cancer research.											
Rationale	 to curate and publish their personal data in a secure environment, generating an interoperable and reusable personal medical record that can be used in clinical care to improve patient outcomes and to support data driven clinical research. The assessment study will help to determine whether the AIDAVA intelligent virtual assistant is 1. effective in improving data curation and publishing process against existing practices, 2. usable and acceptable by patients - with different levels of health, digital and data literacy - and expert data curators, whenever their input is required, 3. valuable for "data users" such as cardiovascular treating physicians and breast cancer clinical researchers. The efficacy of AIDAVA virtual assistant will be influenced by the quality of the different data curation tools (supporting automation) and by the explainability module (managing the human computer interaction). The study will help identify how these components impact the effectiveness of the device. 											
	The results of the study will be used to inform the exploitation plan of the prototype, and the needed improvement to bring a final device to the market.											
Overall Design	 Three arms, prospective cohort-study involving 30 patients per site, 15 Breast Cancer (BC) and 15 cardiovascular (CVD) + 3 experienced data curator per site based on already collected health data, available across different data sources with 3 arms: one for patients assessing the prototype across the 2 generations⁶, one for the patients assessing the prototype only for a single generation, and one for the expert curators (assessing the prototype across the 2 generations) across 4 epochs (see Figure 1) Epoch 1: 1 week duration, takes place just before deployment and evaluation of Generation 1 (G1) of the prototype; it will allow to gather information from the curator on the current situation. 											
	 Epoch 2: 2 weeks duration per patient during period of July - September 2024: assessment of G1, by ingesting personal health data into the prototype and curating them 											

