5.4 Screen Failures

A screen failure occurs when a participant who has consented to participate in the study is not subsequently participating in the study.

A minimal set of screen failure information is required to ensure transparent reporting of screen failure participants. This includes

- demography: age, gender, education level, user profile
- eligibility criteria
- screen failure details: known explanation for failure
- and any concern related to study

As mentioned above, approximately up to 50 patients will be screened - per site/ therapeutic area - to ensure we can enrol 15 patients in the study.

Individuals who do not meet the criteria for participation in the study (screen failure) will not be rescreened.

6. Study Intervention(s)

The objective of collecting these data is to demonstrate that AIDAVA is capable to integrate - and curate - data generated by the patients, as well as data generated by the Health Care Providers (hospital staff and GP) and therefore ensure a complete view of the patient records. The data collected through the personal apps and medical devices will not be used for clinical decision making.

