9.3 Statistical Analyses

Three tests have be retained

- **Paired t-test**: statistical test that compares the means of two related groups, where each subject is measured at two different time points or under two different conditions. It is used to determine if there is a significant difference between the two groups.
- Mann-Whitney U test (unpaired t-test): non-parametric statistical test used to compare the medians of two independent groups. It is often used when the data are not normally distributed or when the sample sizes are small.
- Wilcoxon signed-rank test: non-parametric statistical hypothesis test used to compare two populations with two matched samples.

Primary Endpoint(s) Analysis

The endpoints are defined in Section 9.2 will be used to support the analysis

Computed	Description of measures	Test & meaning (per H1)			
	Population: Expert Curators				
E1	Difference between data points 1 and 2: E1.M2.1△ = M2.1@PDP1 - M2.1@PDP2 E1.M2.2△ = M2.2@PDP1 - M2.2@PDP2	Paired t-test H1: less time spent in curation in G1 than in G0 for expert curators			
E2	Difference between data points 2 and 3: E2.M1-Δ = M1@PDP2 - M1@PDP3	Paired t-test H1: G2 is more usable than G1 for expert curators			
	E2.M2.1∆ = M2.1@PDP2 - M2.1@PDP3 E2.M2.2∆ = M2.2@PDP2 - M2.2@PDP3	H1: less time spent in curation in G2 than in G1 for expert curators			
	Population:	Patients			
P1	Difference in data points 4 and 5 (i.e. difference between G1 and G2 for arm where patients used G1 AND G2)	Paired t-test (effect of system + training/experience from G1)			
	P1.M1- = M1@PDP4 - M1@PDP5	H1: G2 more usable than G1			
	P1.M2.x∆ = M2.x@PDP4 - M2.x@PDP5	H1: G2 requires less time for curation than G1 H1: G2 enables curation with less human intervention than G1			
	P1.M3-∆ = M3@PDP4 - M3@PDP5	H1: G2 provide same or higher quality than G1			
P2	Difference in data points 6 and 7 (i.e. difference between G1 and G2 for arm where patients used G1 OR G2)	Unpaired t-test (effect of system only)			
	P2.M1- = M1@PDP6 - M1@PDP7	H1: G2 more usable than G1			
	P2.M2.x∆ = M2.x@PDP6 - M2.x@PDP7	H1: G2 requires less time for curation than G1 H1: G2 enable curation with less human intervention than G1			
	Ρ2.Μ3-Δ = M3@PDP6 - M3@PDP7	H1: G2 provide same or higher quality than G1			

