A1	Sum across patient arms for G1 A1.M1 = M1@PDP4 + M1@PDP6 A1.M2.x = M2.x@PDP4 + M2.x@PDP6 A1.M3.x = M3.x@PDP4 + M3.x@PDP6 A1.M4.x = M4.x@PDP4 + M4.x@PDP6	Descriptive Statistics Performance in G1 of the AIDAVA system.			
A2	Sum across patient arms for G2	Descriptive Statistics			

Computed	Description of measures	Test & meaning (per H1)
	A2.M1 = M1@PDP5 + M1@PDP7 A2.M2.x = M2.x@PDP5 + M2.x@PDP7 A2.M3.x = M3.x@PDP5 + M3.x@PDP7 A2.M4.x = M4.1@PDP5 + M4.x@PDP7	Performance in G2 of the AIDAVA system.
A3	Difference in A1 and A2 (i.e. difference between G1 and G2 across all patients)	Unpaired t-test
	Α3.Μ1-Δ = Α1.Μ1 - Α2.Μ1	H1: G2 more usable than G1
	A3.M2.xΔ = A1.M2.x - A2.M2.x A3.M3.x-Δ = A1.M3.x - A2.M3.x	H1: G2 requires less time for curation than G1 H1: G2 enable curation with less human intervention than G1
	A3.M4.X-∆ = A1.M4.x - A2.M4.x	Wilcoxon signed-rank test H1: The NLP system developed in G2 yields a higher precision than the NLP system from G1. H1: The NLP system developed in G2 yields a higher recall than the NLP system from G1.
A4	Difference in P1 and P2 (difference between the 2 patient arms)	Unpaired t-test (effect on training/experience) There is a difference in performance due to training/experience with the system : patients having used G1 are more/not more effective in G2 than patients who work with only one generation of the prototype (G1 or G2)
	Α4.Μ1-Δ = P1.Μ1-Δ - P2.Μ1-Δ	H1: G2 more usable than G1 (due to experience during G1)
	A4.M2.x-Δ = P1.M2.x-Δ - P2.M2.x-Δ A4.M3.x-Δ = P1.M3.x-Δ - P2.M3.x-Δ	H1: G2 requires less time for curation than G1 as patients are more experienced H1: There are less questions of the system unanswered during G2 than in G1 as the patient acquired experience in G1
	A4.M4	Not useful

Secondary Endpoint(s) Analysis

Description of measures	Test & meaning (per H1)
Breast Canc	er
Difference in data points 0 and 1 (i.e. difference between G0 and G1 across a sample of 15 patients) U0.TBCx- Δ = TBCx@SDP0 - TBCx@SDPA U0.EBCx- Δ = EBCx@SDP0 - EBCx@SDP1 U0.ACCx- Δ = ACCx@SDP0 - ACCx@SDP1	Unpaired t-test H1: G2 has more (or same) accuracy than G1 while keeping the same time saving and duration
	Descriptive Statistics around performance in G1 of the AIDAVA system (e.g. mean,)

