9.4 Sample Size Determination

We expect a minimum of 15 patients per site and per use case, for a total of 90 patients and 12 data curators across the 2 use cases.

The main objective of the study is to assess performance and acceptance of the AIDAVA prototype and provide evidence that the overarching approach - and underlying tools - can open to new possibilities in data quality enhancement and FAIRification of the data. For this proof of concept study, it is assumed that between 50 to 80 subjects will be sufficient. As we expect some drop out between the 2 epochs of the study, for G1 and for G2 of the prototype, we targeted a higher number than needed.

	Use case 1 Health record of cardiac patients	Use case 2 Breast Cancer Patient registry		
NEMC -	15 patients	15 patients		
MIDATA	+3 expert data curators			
MedUniGraz -	15 patients	15 patients		
MIDATA	+3 expert data curators			
MUMC+/Maastro -	15 patients (MUMC)	15 patients (Maastro)		
DIGI.me	+3 expert data curators			
TOTAL	45 patients	45 patients		
	+ 9 expert data curators			

10. Supporting Documentation and Operational Considerations

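### P2 credits an unadjusted comparison of G1-only with G2-only patients to the system alone, so a shift in site or disease mix between drop-outs and replacements would read as an effect of the tool

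*Protocol*

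**What the plan says.** The synopsis (1.1) describes a cohort "involving 30 patients per site, 15 Breast Cancer (BC) and 15 cardiovascular (CVD". Section 9.4 repeats the quota: "We expect a minimum of 15 patients per site and per use case, for a total of 90 patients". It also says "it is assumed that between 50 to 80 subjects will be sufficient" and "As we expect some drop out between the 2 epochs of the study", without giving a drop-out rate. Section 7.2 says that sites might be asked to recruit new patients if discontinuation is substantial. It does not say from which site or disease group.

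Section 9.3 names three tests: paired t, unpaired (written as Mann-Whitney, with unpaired t in brackets) and signed-rank. Three patient contrasts use the unpaired test:
- **P2:** "Difference in data points 6 and 7 (i.e. difference between G1 and G2 for arm where patients used G1" or G2 only. The table presents it as showing the system's effect and nothing else.
- **A3:** "Difference in A1 and A2 (i.e. difference between G1 and G2 across all patients". The M4 line of A3 names the signed-rank test instead.
- **A4:** P1 minus P2, read as the effect of training or experience.

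None of the three has a stratum or covariate. P1, the paired comparison within returning patients, is not affected by this point.

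**The concern.** P2 is not randomised. G1-only patients are in practice those who left before G2, and G2-only patients are those recruited later. If the two groups hold different proportions of breast cancer and CVD patients, or of sites, their means can differ with no change in the tool.

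The protocol gives good reason to expect the cells to differ:
- **Sources (10.1):** pathology, surgical, multidisciplinary meeting and TNM documents are for breast cancer only. Laboratory, echocardiography, angiography, ambulance, emergency and intensive-care records are for CVD only.
- **Setting (4.4.2):** breast cancer patients are enrolled at a regular hospital visit. First-time CVD patients are enrolled on day 1 of week 1, possibly as inpatients after an infarction.
- **Burden (6.2):** only CVD patients use the blood-pressure device, and they go on using it between generations. Unequal drop-out is therefore plausible.
- **Site (5.1):** three languages and different hospital systems.

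The alternative hypothesis in 9.1 attributes the improvement mainly to the tool and only partly to training. P2 and A4 are the contrasts meant to separate the two, so an error in P2 bears on that attribution for the critical metrics M2 and M3.

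**Working it through.** **Plan's own figure.** 3 sites × 2 use cases × 15 = 90, which agrees with 9.4. The 50 to 80 subjects called sufficient cannot be rederived, because no effect, SD, alpha or power is given.

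**Formula.** With no true tool effect, the absolute bias of the pooled G1–G2 difference is (change in CVD share) × (gap between the disease means). The gap is in within-group SD units. The same holds for site.

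**Assumed inputs (none is in the documents).** 22 drop-outs and 22 replacements, which is 22/90 = 24% of patients; a gap of 0.5 or 1.0 SD; a two-sided 5% level.

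**P2, 22 against 22:**
- CVD 13 → 9: shift 4/22 = 18 points; bias 0.18 × 0.5 = 0.09 to 0.18 × 1.0 = 0.18 SD.
- CVD 14 → 8: shift 6/22 = 27 points; bias 0.27 × 0.5 = 0.14 to 0.27 × 1.0 = 0.27 SD.
- Simulated false-positive rate over these settings: about 5 to 10%. With disease in the model it is about 5%, with bias about 0.

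**P2, 30 against 30 (3,000 simulations per setting).** Each pair gives gap 0.5 SD / gap 1.0 SD:

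| CVD patients, G1-only → G2-only | Bias (SD) | Unadjusted rejection | Adjusted rejection |
|---|---|---|---|
| 15 → 15 | 0 / 0 | 4.0% / 2.7% | 5.1% / 4.8% |
| 18 → 12 | 0.10 / 0.20 | 6.0% / 7.8% | 4.9% / 4.8% |
| 20 → 10 | 0.17 / 0.34 | 8.2% / 18.4% | 5.2% / 4.3% |
| 24 → 6 | 0.31 / 0.61 | 20.9% / 56.8% | 4.9% / 5.4% |

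The Mann-Whitney test gives nearly the same rates as the t-test, so the choice between them does not matter here. The first row shows that with equal mix the unadjusted test is valid but conservative.

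**A3, 90 against 90 with the same 22 replaced.** The shift is diluted to 4/90 = 4.4 or 6/90 = 6.7 points. Bias is 0.044 × 0.5 = 0.02 SD at the least and 0.067 × 1.0 = 0.07 SD at the most. Rejection stays at or below about 5%, and falls to about 1% if the within-patient correlation is 0.5, because A3 treats returning patients as independent. A3 is clearly inflated only under larger shifts. With 30 replaced and the CVD share falling from 50% to 28%, bias is 0.11 to 0.22 SD and rejection 5.8 to 23.8%.

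**A4.** A4 = P1 − P2, so any bias in P2 enters with its sign reversed and would be read as an effect of experience.

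**The case against.** The strongest reply is the enrolment quota. Section 4.4.2 covers first-time patients for both generations and states 15 enrolled per use case, and 9.4 speaks of a minimum of 15 per cell. If every cell were topped up to 15 at G2, G1-only and G2-only counts would match in every cell and the mix could not move. That is correct, and it makes the bias conditional. But 7.2 makes new recruitment only a possibility and names no cell, so the documents do not clearly require such a top-up.

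A second reply is that covariates are usually left to the statistical analysis plan. Here, though, the protocol itself fixes the tests and the causal reading of P2, and a plan that follows 9.3 would inherit both.

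Four stronger readings are tempting but unsupported:
- **That the bias is established.** The protocol gives no disease gap, drop-out rate or mix shift.
- **That the P2 false-positive rates carry over to A3.** They do not, because continuing patients dilute the shift.
- **That every feature differs by country.** One intermediary, MIDATA, serves both Estonia and Austria (5.1).
- **That missing demographics are part of the fault.** Section 5.4 asks for "demography: age, gender, education level, user profile" on screen failures, and the evaluation forms shown do not record age or sex for enrolled patients. However, both are among the curated data (10.5 and 3.2.2), and Form 1 asks about medical and computing education. Collecting more is optional.

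**Conclusion.** The point holds for P2. An unadjusted comparison of drop-outs with replacements cannot carry a label that credits the system alone when nothing clearly holds the site and disease mix. For 22 against 22 patients, a gap of 0.5 to 1.0 SD and a shift of about 20 to 30 points, expect bias of about 0.1 to 0.3 SD and a false-positive rate of about 5 to 10%. Larger shifts are worse; with no shift the loss is only in efficiency. A3 is affected in the same way but weakly (about 0.02 to 0.07 SD in that setting), and A4 through P2. All sizes rest on the stated assumptions, and site effects would add to them. This is a worthwhile and cheap correction, but it does not show that the results will be wrong.

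**What to change.** 1. **P2:** replace the plain unpaired test with a linear model for generation that includes site (3 levels) and therapeutic area (2 levels), or a rank test stratified by them. Both are on the patient curator form. The usability form shows no disease field, but the pseudonym encodes site and disease (10.3.2).
2. **A3 (M1 to M3):** include the same factors and a patient effect for those seen in both generations. Adjusting for the mix alone would leave the test conservative: adjusted rejection was 1.3 to 1.9% at a within-patient correlation of 0.5.
3. **A4:** derive it from that model as the arm-by-generation contrast. As written it subtracts a difference between groups from within-patient differences, so factors cannot simply be added to it.
4. **Wording:** describe P2 as a non-randomised comparison adjusted for site and therapeutic area. The adjustment does not remove other differences between drop-outs and replacements.
5. **Recruitment (7.2):** if feasible, ask that replacements come from the same site and use case as the drop-outs.

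The cost is about three degrees of freedom (2 for site, 1 for therapeutic area) and a short rewrite of the P2, A3 and A4 rows. Additive factors may not fit perfectly, since Dutch breast cancer and CVD patients come from different hospitals. Six separate cells would cost five degrees of freedom and, at 22 per group, leave about 22/6 = 3.7 patients per cell, so they suit a sensitivity analysis.

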Metric 3. Measure quality of data resulting from the data curation & publishing - in terms of their interoperability and reusability	 Metric definition: Data quality score measuring components related to the quality of the personal health knowledge graph and supporting its re-use. This includes dimensions such as volume (number of data items curated), completeness (number of missing items), consistency (number of consistency checks that fail), availability of context information (metadata).
	 Measurement: automatically computed by system at G1 and G2: System computes scores automatically ; formula are being defined in D4.6/Task 4.2 (due date Feb 2024)
Metric 4. Assess the quality/quantity of concepts that can be extracted from clinical narratives with different technologies	 Metric definition: Computed quality of the NLP concept extraction against the manually annotated data ("gold standard") Precision (M4.1): fraction of correct gold standard instances among the retrieved instances Recall (M4.2): fraction of the gold standard concepts that are successfully extracted
	 Measurement 0. Requires a manually annotated gold standard 1. Measure at G0 (current situation): measure # of concepts extracted for registry, manually – in limited time frame (few minutes) 2. Measure at G1 and G2: Precision/Recall for three different NLP systems a. The minimal-effort translation-based system developed for G1 b. The tools with novel DL models developed for G2 c. Measuring generalisation ability to new languages (at G2) The expected outcome is that (b) > (c) > (a). We will measure how well models trained of any two of the three languages (German, Dutch, Estonian) can generalise to the third language as a proxy for how well the overall system can adapt to new languages.

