	1. Data curators spreadsheet (Patient as curator and Exper Form)	t Curator), (in REDCap, Patient Curator FORM; Expert Data Curator

	CVD patients	BC patients
	 Data user/consumers spreadsheet (In REDCap Data use AIDAVA extract IPS and forward it automatically to the H monitoring FORM) 	r/consumer FORM) IDI + enter flag in Data collection and entry forms (REDCap, Patient
VISIT 2 - online W2 Day 1	CVD patients use medical device Check if there is any issue with the medical device (CVD patient only)	
	 Second training session on the prototype - online (open Patient and expert curator curate medical data using All RA fill the patient monitoring form (in REDCap, Patient in Complexity) 	questions) DAVA monitoring FORM)
W2 CVD patient will use medical device		
Day 2-5	 Patient will use AIDAVA and test its functionalities, take Expert curator will curate the data in AIDAVA on deman RA fill the patient monitoring form (in REDCap, Patient in AIDAVA) 	notes and if necessary, will contact helpdesk d. monitoring FORM)
VISIT 3 W2 Day 5	 Second calculation of SMART risk score by AIDAVA and CVD expert Data collection and entry forms: documentation of SMART risk score calculation result and time 	
	 AIDAVA extract IPS and forward it automatically to the HDI (+ enter flag in REDCap, Patient monitoring FORM) Patient and curator will fill in the system usability scale questionnaire online (in REDCap, System Usability Scale - SUS FORM) Data curators spreadsheet (Patient and Expert Curator). (in REDCap, Patient Curator FORM; Expert Data Curator Form) Data user/consumers spreadsheet (In REDCap Data user/consumer FORM) 	
W3		At the end of G1 - across all sites - fires the queries identified as secondary end points; RA reports the results in the data users/consumers spreadsheet (in REDCap Data user/consumer FORM).
End of evaluation	Delete personal patient data and PHKG (after finalisation of evaluation report), but keep evaluation score from G1.	
VISIT 4 - online W4	Feedback to patient	

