9.2 Analysis Sets

Primary endpoint components

The analysis set will include all expert curators and patient participants and will take into account the primary data points (PDP) identified in yellow in the figure below across the 3 arms.

Primary Data Point	Generation	Arm	Description of measures (through RedCap Form and computed)		
PDP1	G0		M2.1 : Estimated time spent in curation per patient record (min)		
PDP2	G1	Expert Curator	M1: System Usability Score M2.1: Estimated time spent in curation per patient record (min)		
PDP3	G2		Same than for G1 - measured for G2		
PDP4	G1	G1 AND G2 users	 M1: System Usability Score M2: Time spent in for curation in min Estimated time in RedCap form (M2.1) Computed "active" time to answer queries (M2.2) Computed amount of data elements curated automatically by system (M2.3) requiring human intervention with answer from the patient (M2.4) 		

Primary Data Point	Generation	Arm	Description of measures (through RedCap Form and computed)
			 without answer the patient and requiring curator input (M2.5) without answer requested from curator but not successful (M2.6)
			M3: Computed data quality scores of curated record in terms of completeness, correctness, consistency and trustworthiness (as detailed in Task 4.6).
			 M4: Computed quality of the NLP concept extraction against the manually annotated data ("gold standard") Precision (M4.1) which measures the fraction of gold standard instances among the retrieved instances Recall (M4.2) which measures the fraction of the gold standard concepts that could successfully be retrieved
PDP5	G2		Same than PDP4 - for G2
PDP6	G1	G1 OR G2	Same than PDP4 - for G1
PDP7	G2	users	Same than PDP5 - for G2

Secondary endpoints

The analysis set will include all data users (BC specialists and CVD experts) and will take into account the secondary data points (SDP) identified in orange in the figure below across the patient arms. As indeed this is about reuse of data, after the curation process; there is no effect expected from the fact that patients did use G1 before G2 or not.

Secondary Data Point	Generation	Arm	Description of measures (through RedCap Form and computed)		
			Breast Cancer		

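### The G1–G2 test of NLP precision and recall (M4) applies a matched-sample test to partly unmatched patient pools with different records, so it cannot isolate the NLP system

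*Protocol*

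**What the plan says.** Section 3.1 (Metric 4) treats M4 as a property of software. It says "Requires a manually annotated gold standard" and then "Measure at G1 and G2: Precision/Recall for three different NLP systems": the translation-based G1 system, the G2 tools, and a test of generalisation to a new language. No patient arm is named there.

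Section 9.2 places M4 among the measures of the patient arms. Under PDP4 (patients who use both generations) it lists the "quality of the NLP concept extraction against the manually annotated data". PDP6 (single-generation patients) is "Same than PDP4 - for G1", and PDP5 and PDP7 repeat the set for G2.

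Section 9.3 pools over arms: "A1.M4.x = M4.x@PDP4 + M4.x@PDP6" for G1, with the matching sum of PDP5 and PDP7 for G2. Row A3 takes the difference, described as "i.e. difference between G1 and G2 across all patients", and assigns M4 the Wilcoxon signed-rank test. The hypothesis is "H1: The NLP system developed in G2 yields a higher precision than the NLP system from G1", with a parallel one for recall. At its start, Section 9.3 describes the signed-rank test as one for matched samples.

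Section 4.1 defines an arm of patients who evaluate only G1 or only G2, and a gap of 16 to 18 months between generations. Section 4.4.4 has returning patients' data uploaded from scratch at G2. Section 9.1 names M2 and M3 as the critical metrics and calls M4 less critical.

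**The concern.** A claim that one NLP system beats another needs both systems scored on the same documents. Otherwise a difference in precision or recall may reflect easier or harder text. Row A3 builds the contrast from patients, not documents. Some patients contribute to one generation only, and the rest contribute a record that has had 16 to 18 months to grow.

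At stake is one of the four primary metrics. A gain could be credited to the G2 tools when the text changed, or a real gain could be hidden. The stated test also cannot be run on the pools as defined, so an analyst would have to improvise.

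**Working it through.** The protocol gives no planned effect, SD, alpha or power for M4, so there is no M4 figure to reproduce. The one nearby number does reproduce: 15 patients × 2 use cases × 3 sites = 90 (Section 9.4).

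**1. What is being compared.** In Section 3.1 the unit is the NLP system. In Section 9.3 the G1 pool is PDP4 + PDP6 and the G2 pool is PDP5 + PDP7, so the unit is the patient. The A3 hypothesis is about systems, so it does not match the quantity computed.

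**2. Is the sample matched?** Only patients at both PDP4 and PDP5 form pairs. If R of 90 G1 patients return, there are R pairs and 90 − R unmatched G1 patients. Return of 80%, 60% or 50% (assumed) gives:

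- 72 pairs, 18 unmatched
- 54 pairs, 36 unmatched
- 45 pairs, 45 unmatched

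The signed-rank test cannot use the unmatched patients, nor any new G2-only patients, which Section 7.2 allows for. In the same A3 row, M1 to M3 are tested on these pools with an unpaired t-test. The same pools are thus treated as independent for three metrics and matched for the fourth.

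**3. Does pairing by patient rescue it?** For a returning patient, the expected G2 − G1 difference is the system effect plus the document shift. Pairing removes stable patient differences but not that shift.

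Illustration with identical systems, so that every rejection is false (two-sided alpha 0.05; shift δ and SD assumed). For an unpaired comparison with n per generation, SE = SD × √(2/n), and P(reject) = Φ(δ/SE − 1.96) + Φ(−δ/SE − 1.96). With SD 0.10 and n = 90, SE = 0.10 × √(2/90) = 0.0149. At δ = 0.02, δ/SE = 1.34 and P = 0.27.

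| Analysis | δ = 0.02 | δ = 0.03 | δ = 0.05 |
|---|---|---|---|
| Unpaired, SD 0.10, n = 90 | 27% | 52% | 92% |
| Unpaired, SD 0.15, n = 90 | 15% | 27% | 61% |
| Unpaired, SD 0.10, n = 50 | 17% | 32% | 71% |
| Signed-rank, 50 returning pairs | 27% | 53% | 93% |
| Signed-rank, 90 returning pairs | 47% | 78% | 99.7% |

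The signed-rank rows are simulated (1,500 runs). They use SD 0.10 and within-patient correlation 0.5, so the SD of the difference is 0.10 × √(2 × 0.5) = 0.10.

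**4. Same documents for both systems.** The shift is zero by design. The simulated signed-rank rejection rate is then 4.1%, 5.8% and 5.2% for 50, 80 and 90 pairs, close to the nominal 5%.

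Pairing by document also helps precision. With an assumed per-document SD of 0.10 and 60 documents, the SE is 0.10 × √(2/60) = 0.018 on different documents. On the same documents it is 0.10 × √(2 × (1 − 0.6)/60) = 0.012 at correlation 0.6, and 0.014 to 0.008 for correlations 0.4 to 0.8. This is a gain in precision and does not measure the bias.

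**The case against.** The strongest reply is that M4 was always meant as a benchmark on a fixed corpus. Section 3.1 compares systems, M4 is absent from the patient contrasts P1 and P2, row A4 marks it as not useful, and it alone receives the signed-rank test. The protocol never says outright that the gold standard is made from study patients' narratives. That much stands. But on a fixed corpus one system has one set of scores, so separate M4 values at PDP4 and PDP6 and a sum over them would have no meaning. Sections 9.2 and 9.3 therefore cannot be followed under that reading. Because the protocol itself fixes the data points, pools and test, this is not detail left to an analysis plan.

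Two stronger readings are tempting but not supported.

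- A reader might infer that M4 cannot be computed, because no visit or form includes annotation. Section 3.1 does require a gold standard, Section 9.2 labels M4 as computed, and corpus annotation is not a patient procedure. Section 5.1 describes annotation of texts for training sets.
- A reader might infer that the G2 system can never be run on G1 documents, because Section 4.4.2 says "Delete personal patient data and PHKG (after finalisation of evaluation report), but keep evaluation score from G1". The End-of-Study section keeps the curated record to the end of the project, and the data disposal entry in Annex 4 deletes transferred data only then. These statements conflict. Returning patients' older narratives could also come back with the G2 upload, so their two records probably overlap substantially. Only single-generation patients have wholly different records.

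It is also fair that Section 9.1 gives M4 less weight than M2 and M3.

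**Conclusion.** The point holds as a conflict between Section 3.1 and Sections 9.2/9.3. As written, the A3 contrast for M4 is either not a valid paired test, because the pools contain unmatched patients, or it mixes NLP system with document set. Either way it cannot support its hypothesis.

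The structural conclusion rests on the protocol's text alone. The size does not: the real document shift and spread are not given, and the 15% to 99.7% range is illustrative only. The shift could also act in either direction. The change should be made, but it concerns the metric that the protocol itself treats as less critical.

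**What to change.** In Sections 3.1, 9.2 and 9.3:

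- Base the M4 hypothesis test on one fixed, annotated, held-out document set per language (German, Dutch, Estonian), not used for training.
- Run the G1 system, the G2 system and the cross-language models on that same set, and apply the signed-rank test already named, paired by document.
- Take the M4 test out of the pooled A3 contrast. Any M4 obtained on study patients' records can stay in A1 and A2 as description only.
- Reconcile the statements on when patient data are deleted (Section 4.4.2, End-of-Study, Annex 4 data disposal).

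The cost is protocol wording, a re-run of the G1 pipeline on the held-out set, and some annotated documents kept out of training. No patient visit or form changes.
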